5.4.2.7. HBV Virologic Breakthrough

5.4.2.7.1. Definition

HBV virologic breakthrough is defined as having a confirmed on-treatment HBV DNA increase by $>1 \log_{10}$ from nadir level (lowest level reached during treatment) in participants who did not have on-treatment HBV DNA level $< \text{LLOQ}$ or a confirmed on-treatment HBV DNA level $>200 \text{ IU/mL}$ in participants who had on-treatment HBV DNA level $< \text{LLOQ}$. Confirmed HBV DNA increase/level means that the criterion should be fulfilled at 2 or more consecutive time points or at the last observed on-treatment time point.

On-treatment will be defined as the time period in which the participant receives any of the study interventions (JNJ-3989 and/or JNJ-6379 and/or NA and/or PegIFN- α 2a).

The number and proportion of participants who experience a virologic breakthrough will be summarized descriptively by analysis phase.

The number and proportion of participants who experience a virologic breakthrough followed by on-treatment biochemical flare will be summarized descriptively.

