### **6.6.2. NA Re-treatment Criteria and Monitoring after Stopping of NA**

Participants who meet the NA treatment completion criteria outlined in Section [6.6.1](#) will be monitored closely during the follow-up phase.

After stopping NA treatment, participants should be monitored as follows:

- Regular monitoring visits will be every 4 weeks during the follow-up phase in accordance with the [Schedule of Activities](#).

- A post-treatment HBV DNA value of >20,000 IU/mL should trigger re-testing of ALT/AST, HBV DNA, and total and direct bilirubin within a maximum of 7 days from receipt of the data and further repeats as necessary (ie, weekly until HBV DNA returns to <20,000 IU/mL).
- A post-treatment HBV DNA value of >2,000 IU/mL (but <20,000 IU/mL) should trigger a re-test within 14 days from receipt of the data and further repeats as necessary (ie, every other week until HBV DNA returns to <2,000 IU/mL).
- A post-treatment ALT value of >5x ULN should trigger re-testing of ALT, AST, ALP, total and direct bilirubin, INR, albumin, and HBV DNA on a weekly basis until ALT and AST levels have returned to <5x ULN.

After stopping NA treatment, participants should re-start NA treatment:

- Immediately with signs of decreasing liver function based on laboratory findings (eg, INR, direct bilirubin) or clinical assessment (eg, ascites, hepatic encephalopathy),
- Immediately with an HBV DNA value of >100,000 IU/mL (irrespective of confirmation and/or ALT increase).
- With confirmed post-treatment HBeAg seroreversion (HBeAg positive after it was negative at NA completion)
- With confirmed\* post-treatment increases in HBV DNA >2,000 IU/mL and ALT >5x ULN
- With confirmed\* post-treatment increases in HBV DNA >20,000 IU/mL.

*\* At least 4 weeks apart frequency of visits as described above*

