5.1.3. On-Treatment and Off-Treatment Period

The on-treatment period begins with the first drug intake and finishes with the maximum between:

- Last dose of NA + 2 days
- Last dose of PegIFN- α 2a +10 days
- Last dose of JNJ-3989 + 28 days

The off-treatment period starts after the end of on-treatment period and stops if the NA re-treatment starts.

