5.4.2.6. Flares

5.4.2.6.1. Definition

The criteria based on blood markers/lab tests for each of the flare types are defined as below.

1. **Virologic flare** is defined as follows:

Derivation 1. This derivation of virologic flare will be assessed only for those participants who are off-treatment and had $\text{HBV DNA} < \text{LLOQ}$ at the last observed point on-treatment.

The start date of a confirmed virologic flare is defined as the first date of two consecutive visits with $\text{HBV DNA} > 200 \text{ IU/mL}$. The end date of the same confirmed virologic flare is defined as the first date when HBV DNA value returns to $\leq 200 \text{ IU/mL}$ or the date of NA treatment restart, whichever comes first. Each virologic flare will be categorized based on the confirmed (i.e., two consecutive values) peak HBV DNA above any of the three thresholds within the start and end date of that flare as follows: 20,000 IU/mL , 2,000 IU/mL , and 200 IU/mL .

- 1 (Yes) = confirmed** $\text{HBV DNA} >$ peak threshold.
- 0 (No) = at least one off-treatment HBV DNA measurement available and not meeting the criteria of confirmed $\text{HBV DNA} >$ peak threshold.
- 2 (Not applicable) = no off-treatment HBV DNA quantitative measurements available.

Derivation 2. This derivation of virologic flare will be assessed only for those participants who are off-treatment and had $\text{HBV DNA} \geq \text{LLOQ}$ at the last observed point on-treatment.

The start date of a confirmed virologic flare is defined as the first date of two consecutive visits with HBV DNA log_{10} increase $> 1 \log_{10}$ from EOT. The end date of the same confirmed virologic flare is defined as the first date when HBV DNA log_{10} increase from end of treatment returns to $\leq 1 \log_{10}$ or the date of NA treatment restart, whichever comes first. Each virologic flare will be categorized based on the confirmed (i.e., two consecutive values) peak HBV DNA increase above any of the three thresholds within the start and end date of that flare as follows: $1 \log_{10}$, $2 \log_{10}$, $3 \log_{10}$.

- 1 (Yes) = confirmed** HBV DNA increase from EOT $>$ peak threshold
- 0 (No) = at least one off-treatment HBV DNA measurement available and not meeting the criteria of confirmed HBV DNA increase from EOT $>$ peak threshold.
- 2 (Not applicable) = no off-treatment HBV DNA quantitative measurements available.

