- 0 (No) = otherwise

^{**} Confirmed means that the criterion should be fulfilled at 2 or more consecutive time points or at the last observed time point.

The virologic and clinical flares will be assessed only off-treatment, while biochemical flares will be identified on-treatment and off-treatment, respectively. On-treatment virologic flares are described as virologic HBV breakthrough in Section 5.4.2.7.

On-treatment will be defined as the time periods in which the participant receives any of the study interventions (JNJ-3989 or JNJ-6379 or NA or PegIFN- α 2a). Off-treatment will be defined as the

periods when the participants do not receive any of the study interventions (JNJ-3989, JNJ-6379, NA, and PegIFN- α 2a).

The incidence rate will be calculated and summarized for each type of on-treatment or off-treatment flares (virologic, biochemical and clinical) separately, as well as the overall incidence of participants experiencing at least one flare, regardless of type. Additionally, for each participant the total number of flares the participant experienced will be counted by type. Such counts will be used to summarize the distribution of the total number of flares by type and by study panel.

For on-treatment biochemical flares, the incidence of flares causing treatment discontinuation will be summarized. Further, for off-treatment flares, the count and percentage of participants who experienced a flare followed by NA re-treatment will be summarized by flare type. Similarly, the incidence of flares followed by the achievement of HBsAg seroclearance (at any time) will be summarized by flare type.

Flares that are associated with signs of liver decompensation will be provided in a listing.

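### SAP 5.4.2.7.1 does not exclude NA re-treatment from on-treatment time, so residual viraemia after an NA restart can be counted as a follow-up-phase virologic breakthrough

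*SAP*

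**What the plan says.** SAP 5.4.2.7.1 defines breakthrough by two limbs. If on-treatment HBV DNA was never below LLOQ, a confirmed rise of more than 1 log10 from nadir is needed. The other limb applies "in participants who had on-treatment HBV DNA level" below LLOQ, and there the test is a fixed level: confirmed on-treatment HBV DNA above 200 IU/mL. Confirmation means that "the criterion should be fulfilled at 2 or more consecutive time points or at the last observed on-treatment time point". The section then states its own time frame: "On-treatment will be defined as the time period in which the participant receives any of the study interventions", listing JNJ-3989, JNJ-6379, NA and PegIFN-α2a. NA re-treatment is neither named nor excluded. Counts are given by analysis phase.

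The flare section, SAP 5.4.2.6.1, uses the same idea in the plural: "On-treatment will be defined as the time periods in which the participant receives any of the study interventions". Off-treatment is then time on none of them, and on-treatment virologic flares are referred to the breakthrough section. An off-treatment virologic flare closes when HBV DNA returns to its threshold "or the date of NA treatment restart, whichever comes first".

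SAP 5.1.3 is different. "The on-treatment period begins with the first drug intake and finishes with the maximum between" last NA dose plus 2 days, last PegIFN-α2a dose plus 10 days and last JNJ-3989 dose plus 28 days. After that, "The off-treatment period starts after the end of on-treatment period and stops if the NA re-treatment starts". It does not say that on-treatment time resumes.

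Protocol 6.6.1 makes HBV DNA below LLOQ a condition for completing NA. Among the restart triggers in Protocol 6.6.2 is "Immediately with an HBV DNA value of >100,000 IU/mL (irrespective of confirmation and/or ALT increase". Others are confirmed values above 20,000 IU/mL, and confirmed values above 2,000 IU/mL with ALT above 5x ULN.

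**The concern.** The protocol objective is the frequency of breakthrough during study intervention, that is, loss of viral control under therapy. The limb that applies to participants who stopped NA under the completion criteria is a level and not a rise. It therefore cannot tell HBV DNA that is climbing on treatment from HBV DNA that is falling after a restart. If re-treatment counts as on-treatment, rebound after planned NA withdrawal can be reported as failure of treatment. In the follow-up-phase count such cases would sit beside true breakthroughs in participants who never stopped NA, and the table would not separate them. Some could also enter the summary of breakthrough followed by an on-treatment biochemical flare, if the ALT/AST flare itself starts after restart.

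**Working it through.** There is no plan figure to reproduce. The check compares the definitions and then applies the breakthrough rule to a restarted participant.

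**1. Does the text include re-treatment?** Under 5.4.2.7.1 and 5.4.2.6.1, status follows receipt of drug, so time on restarted NA is on-treatment. SAP 5.6.1 also counts re-treatment weeks as NA exposure in follow-up. Where the SAP wants re-treatment out it says so: the multiple-marker thresholds (5.4.2.4.9), functional cure (5.4.2.5) and the end of a virologic flare (5.4.2.6.1). Section 5.4.2.7.1 has no such wording. In 5.1.3 the last NA dose must mean the first course, since otherwise no off-treatment period could precede re-treatment. Re-treatment time then belongs to neither period. The SAP does not say which section governs breakthrough.

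**2. Which limb applies?** A participant who stopped NA under Protocol 6.6.1 had HBV DNA below LLOQ on treatment, so the 200 IU/mL limb applies.

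**3. How long does HBV DNA stay above 200 IU/mL after restart?** The fall needed is log10(HBV DNA at restart / 200):
- from 2,000: log10(10) = 1.0
- from 20,000: log10(100) = 2.0
- from 100,000: log10(500) = 2.70

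The documents give no rate of decline after an NA restart. As an assumption, take a linear fall of 3.5 log10 per 12 weeks (0.292 per week). Protocol 2.2.2.1 reports a mean fall of more than 3.5 log10 at Week 12 in not-currently-treated participants on JNJ-6379 alone, and a similar fall in those given JNJ-6379 or placebo with an NA. A faster 5.0 log10 per 12 weeks (0.417 per week) is shown as well. Weeks to 200 IU/mL = fall needed / weekly rate. The last two columns count the samples after restart that are still above 200 IU/mL.

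| HBV DNA at restart (IU/mL) | Assumed fall per 12 weeks | Weeks to 200 | Sampled 4-weekly | Sampled 2-weekly |
|---|---|---|---|---|
| 2,000 | 3.5 log10 | 3.4 | 0 | 1 |
| 2,000 | 5.0 log10 | 2.4 | 0 | 1 |
| 20,000 | 3.5 log10 | 6.9 | 1 | 3 |
| 20,000 | 5.0 log10 | 4.8 | 1 | 2 |
| 100,000 | 3.5 log10 | 9.3 | 2 | 4 |
| 100,000 | 5.0 log10 | 6.5 | 1 | 3 |

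With two consecutive values required, a restart at 100,000 is scored in three of four cases, at 20,000 only with 2-weekly sampling, and at 2,000 in none. Three things could add cases: a restart-day sample counted as on-treatment, a single last observed value above 200, or weekly retests counted as time points. For the last, weekly values after a restart at 2,000 would be about 1,020 and 520 at the slower rate and 770 and 290 at the faster one, all above 200.

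**4. Size per case.** 1/24 = 4.2 percentage points overall and 1/12 = 8.3 in a panel, taking the target numbers as denominators.

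**The case against.** The strongest reply is that 5.1.3 already settles the matter. SAP Amendment 1 added it to define these periods; it gives a single on-treatment period, and on-treatment is not said to resume at restart. The wording in 5.4.2.7.1 is singular, and the SAP treats re-treatment as its own category, with a separate CRF page (5.4.2.5) and separate summaries (5.4.2.4.7 and 5.4.2.4.8). This shows that the intention may well have been to exclude re-treatment. It does not remove the problem. Section 5.1.3 never says that it overrides the endpoint's own definition, and someone programming from 5.4.2.7.1 would include re-treatment.

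Four stronger readings are tempting, and the documents do not support them.
- A reader might infer that every restarted participant is scored. Scoring depends on HBV DNA at restart, rate of fall and sampling. The weekly and two-weekly retests in Protocol 6.6.2 concern values after stopping NA, and nothing says whether they continue after restart. SAP 5.1.2 does not clearly say whether extra retests count as time points for confirmation.
- A reader might infer that everyone who stops NA was below LLOQ. After early discontinuation, Protocol 7.1 allows NA to be stopped on investigator judgement.
- A reader might infer that the breakthrough rate for the 48-week intervention phase is inflated. SAP 5.1.1 places re-treatment in the follow-up phase, and the table is split by phase.
- A reader might infer that the same event is counted twice. The virologic flare closes at restart and is tabulated separately. The same viraemia can carry two labels in turn, but it is not counted twice in one table. An ALT/AST flare that began before restart stays off-treatment by its start date.

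It is also fair that few participants may be involved. Protocol Appendix 10 (Amendment 4 rationale) cites 19.1% meeting the NA completion criteria with JNJ-3989 200 mg in an earlier Phase 2b study. Applied here as an illustration, 0.191 x 24 = 4.6 would stop NA, and only some of them would restart at high HBV DNA.

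**Conclusion.** The point stands as an unresolved conflict between 5.4.2.7.1 and 5.1.3 that, on the literal endpoint text, allows a wrong classification. A participant who stopped NA below LLOQ, rebounded and restarted can be reported as a follow-up-phase breakthrough while NA is working. This is likely after a restart at more than 100,000 IU/mL and uncertain at the lower triggers. Each case moves the follow-up-phase rate by about 4 points overall or 8 in a panel; the open-label count does not change. The likelihoods rest on assumed linear declines of 3.5 to 5.0 log10 per 12 weeks and on sampling every 2 or 4 weeks. The conflict between the definitions does not depend on those assumptions. The analysis is descriptive and no test is affected, but the correction is cheap and worth making.

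**What to change.** In SAP 5.4.2.7.1, state that on-treatment for breakthrough means the initial treatment course, up to the first stop of all study interventions, and excludes NA re-treatment. Participants who never stop NA then remain on-treatment through follow-up, as they should.

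Reconcile this with 5.1.3, and do not import its date rule unchanged. The Week 44 injection may be given up to 3 weeks late (Protocol 6.4), and 28 days after Week 47 is Week 51, whereas NA may have stopped at Week 48. Rebound in those weeks would count as on-treatment. Also assign re-treatment time explicitly in 5.1.3, and say whether unscheduled retests count as time points for confirmation.

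If rises during re-treatment are of interest, report them separately as a confirmed increase of more than 1 log10 from the nadir reached after restart.

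Do not apply the exclusion to biochemical flares. Under 5.4.2.6.1 an off-treatment flare must start while no intervention is received, so a flare starting during re-treatment would fall in neither class and drop out of the tables. Keep these flares as a separate category.

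The cost is one sentence in 5.4.2.7.1, a matching edit to 5.1.3, a date condition in the derivation and one extra flare category. No new data are needed and clinical management does not change.

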5.4.2.8. HBV-Specific T-Cells Response

Descriptive statistics (for example, may include n, mean, SD, CV, geometric mean, median, minimum, and maximum) will be used to describe the magnitude of the IFN- γ T cell response or the CD4+ and CD8+ T-cell responses (expressing at least 1 cytokine such as IL-2, TNF- α or IFN- γ specific to any HBV antigen) as defined by ELISpot and/or ICS, respectively. Changes from baseline (if present) will also be tabulated for PBMCs during study intervention and follow-up. The proportion (%) of CHB participants with positive responses based on the magnitude of the IFN- γ T cell response or the CD4+ or CD8+ T cells expressing at least 1 of the cytokines amongst

IL-2, TNF- α or IFN- γ for 1 of the HBV antigens as defined by ELISpot and/or ICS, respectively, will be determined.

Graphs showing the individual subject values as dots, together with horizontal lines indicating the corresponding median and interquartile range (IQR) per time point for each assay will be presented. The spaghetti plots will be used to show the patient profiles per time point for each assay. A graph showing the median and IQR over time will be presented. A bar chart will be used to show the breadth of response (i.e., HBV-specific immune response rate for combinations of peptide pools).

For intracellular cytokine staining (ICS), for all cytokine combinations (IFN γ and/or TNF α and/or IL-2), pie charts will be presented to reflect the distribution of each of the cytokine combinations (i.e., the proportion of a specific cytokine combination of the CD4 or CD8 T-cells secreting at least one cytokine), and bar charts will be presented to reflect the mean magnitude of each combination.

5.4.3. Subgroup Analyses

The same subgroups as described in Section 5.3.1.3 may be used to analyze key secondary endpoints.

5.5. Exploratory Endpoints Analysis

5.5.1. Relationship Between Intrahepatic and Blood Markers

Relationships between intrahepatic and blood markers (Table 4) and/or their change from baseline at Week 40 will be evaluated graphically with scatter plots displaying individual associations.

Means on pooled individual data by study panel and overall mean will also be plotted on the same graph.

The following correlation coefficients will be calculated by study panel and overall for the different correlation scenarios:

- Pearson's correlation coefficient for two continuous variables.
- Phi correlation coefficient for two binary variables.
- Point biserial correlation coefficient for one binary variable and one continuous variable.

Potential relationship on the selected subgroups defined in Section 5.7.4 will also be explored using the same graphical approach.

The following markers will be considered, i.e., each intrahepatic marker will be plotted against each blood marker:

Table 4: List of Intrahepatic and Blood Markers of Interest

Intrahepatic Markers/Endpoints	Blood Markers/Endpoints
• Proportion of HBsAg+ hepatocytes at Week 40	• HBV DNA level at Week 40 (\log_{10})
• Change from Baseline at Week 40 in proportion of HBsAg+ hepatocytes	• HBV RNA level at Week 40 (\log_{10}) • HBsAg level at Week 40 (\log_{10})

 • Proportion of cccDNA-positive hepatocytes at Week 40 • Change from Baseline at Week 40 in proportion of cccDNA-positive hepatocytes • Proportion of pgRNA-positive hepatocytes at Week 40 • Change from Baseline at Week 40 in proportion of pgRNA-positive hepatocytes • pgRNA levels at Week 40 (\log_{10} copies/ cell) • Change from Baseline at Week 40 in pgRNA levels (\log_{10} copies/ cell) • 	
 • HBeAg level at Week 40 (\log_{10}) • HBcrAg level at Week 40 (\log_{10}) • Change from Baseline at Week 40 in HBV DNA (\log_{10}) • Change from Baseline at Week 40 in HBV RNA (\log_{10}) • Change from Baseline at Week 40 in HBsAg (\log_{10}) • Change from Baseline at Week 40 in HBeAg (\log_{10}) • Change from Baseline at Week 40 in HBcrAg (\log_{10}) • Maximum on-treatment ALT decrease • HBsAg seroclearance at FU Week 24
--	---

Additional markers and endpoints may be evaluated when data will be available.

5.5.2. Association Between Baseline Characteristics or Intrahepatic/Blood Markers with Efficacy Variables

The following list of efficacy endpoints of interest will be evaluated:

- Proportion of participants with HBsAg <10 IU/mL at Week 40 (Yes/No)
- Proportion of participants with HBsAg <10 IU/ml at Off-Treatment Week 24 (Yes/No)
- Proportion of participants with HBsAg Seroconversion at Off-Treatment Week 24 (Yes/No)
- Proportion of participants with Functional Cure at Off-Treatment Week 24 (Yes/No)

For each of the endpoints listed above, the potential association with the following selection of characteristics or intrahepatic/blood markers may be assessed:

- Duration of NA (years)
- Age (years)
- Duration of infection (years)
- Baseline HBeAg level (quantitative), for panel 1 only
- Baseline HBV DNA level (\log_{10})
- Baseline ALT Level (quantitative)
- Baseline Peripheral HBsAg level (\log_{10})
- Baseline Number of HBsAg+ hepatocytes (\log_{10})
- Proportion of HBsAg+ hepatocytes at baseline
- Proportion of cccDNA-positive hepatocytes at Baseline
- Proportion of pgRNA-positive hepatocytes at Baseline
- HBeAg level (quantitative) at Week 40

- HBV DNA level (\log_{10}) at Week 40
- ALT Level (quantitative) at Week 40
- Peripheral HBsAg level (\log_{10}) at Week 40
- Proportion of HBsAg+ hepatocytes (\log_{10}) at Week 40
- Proportion of cccDNA-positive hepatocytes at Week 40
- Proportion of pgRNA-positive hepatocytes at Week 40

These lists may be modified based on clinical relevance and data availability.

For Panels 1 and 2, logistic regression models will be performed for each efficacy endpoint of interest, and will include study panel and characteristics/marker of interest as factor, with and without the study panel-by-baseline variable as the interaction-terms. Covariates and/or interaction terms may be added or removed to a given model for fitting purpose.

Odd-Ratios (OR) and corresponding 80% CIs will be also calculated without multiplicity adjustment overall. Statistical analysis of treatment heterogeneity between subgroups will be conducted by assessing the significance of the interaction term. The forest plot will present graphically the on/off treatment efficacy OR estimate and its 80% CI resulting from the model by the prespecified subgroups on the overall population and by study panels.

